4. SELECTION AND WITHDRAWAL OF PATIENTS

Prospective waivers (exceptions) from study inclusion and exclusion criteria to allow patients to be randomized/enrolled are not granted by Teva ([Appendix D](#)).

Standard of care for treatment of CP should continue throughout the study, with some possible restrictions related to concomitant medication, for example, as outlined in Section 5.5. Standard of care could include any possible rehabilitation service(s), such as physiotherapy, occupational therapy, or sensory integration of the patient, which should remain constant throughout the course of the study.

4.1. Patient Inclusion Criteria

Patients may be randomized/enrolled in this study only if they meet all of the following criteria:

1. Patient is 6 through 18 years of age (inclusive) at baseline.
2. Patient weighs at least 26 pounds (12 kg) at baseline.
3. Patient has had CP symptoms since infancy (≤ 2 years), and CP is judged by the investigator to be of a non-progressive nature ([Monbaliu et al 2017](#), [Wimalasundera et al 2016](#)).
4. Patient has a diagnosis of DCP according to the Surveillance of Cerebral Palsy in Europe criteria ([Cans 2000](#)).
5. Patient has an MD-CRS part II total score of ≥ 10 at the baseline visit, based on investigator scoring of chorea.
6. Patient's symptoms are causing functional problems determined by a CGI-S score of 4 or greater based on investigator scoring.
7. Choreiform is the predominant (ie, the main cause of impairment or distress) movement disorder as assessed at screening.
8. Patient is able to swallow study medication whole.
9. Patient and caregiver are willing to adhere to the medication regimen and to comply with all study procedures.
10. Patient is in good general health, as indicated by medical and psychiatric history, as well as physical and neurological examination.
11. In the investigator's opinion, the patient and/or caregiver has the ability to understand the nature of the study and its procedures, and the patient is expected to complete the study as designed.
12. For a patient who is a minor, the parent(s)/legally accepted representative(s) provide written informed consent, and the patient provides assent (in accordance with local regulations). Adult patients provide their own written informed consent (in accordance with local regulations) and the legally acceptable representative will sign, if needed.

In this study, eligible patients are patients with dyskinetic CP who may have some degree of mental, motor, and/or communication (eg, speech, writing, etc) limitations or disabilities. The patient may not be able to read the assent/consent form. Some patients may only be able to provide a limited assent/consent (for instance, by verbalizations or gestures). The investigator will determine the suitability of enrolling such patients in this study and will follow the local regulation to obtain the relevant assent/consent.

13. Caregivers provide written informed consent after being assigned the role by an adult patient, or if this role is delegated by the parent/legally accepted representative of a patient who is a minor.
14. Females who are postmenarchal or ≥ 12 years of age may be included only if they have a negative beta-human chorionic gonadotropin (β -HCG) test at baseline or are sterile. Definitions of sterile, premenarchal, and postmenarchal are given in [Appendix F](#).
15. Females who are postmenarchal or ≥ 12 years of age whose male partners are potentially fertile (ie, no vasectomy) must use highly effective birth control methods for the duration of the study (ie, starting at screening) and for 30 days after the last dose of IMP. Further details are included in [Appendix F](#).

4.2. Patient Exclusion Criteria

Patients will not be randomized/enrolled in this study if they meet any of the following criteria:

1.
 - a. Patient has a predominant movement disorder other than dyskinesia.
 - b. Patient's predominant motor symptoms are dystonic.
 - c. Patient's predominant motor symptoms are spastic.
 - d. Patient has another other movement disorder that could impair the motor assessment in the MD-CRS part II.
 - e. Patient has choreiform movement disorder that has not been consistent throughout the life of the patient.
2. Patient has clinically significant depression at screening or baseline.
 - Note: Patients receiving antidepressant therapy may be enrolled if on a stable dose for at least 6 weeks before screening and anticipated to remain stable (dose and frequency) within the study duration.
3. Patient has a history of suicidal intent or related behaviors based on medical or psychiatric history or the C-SSRS within 2 years of screening:
 - Previous intent to act on suicidal ideation with a specific plan, irrespective of level of ambivalence, at the time of suicidal thought
 - Previous suicidal preparatory acts or behavior
4. Patient has a history of a previous actual, interrupted, or aborted suicide attempt based on medical or psychiatric history or the C-SSRS.
5. Patient has a first-degree relative who has completed suicide.
6. Patient has received any of the following concomitant medications within the specified exclusionary windows of screening:

- Within 30 days: tetrabenazine, deutetrabenazine, or valbenazine
 - Within 21 days: reserpine
 - Within 14 days: levodopa, dopamine agonists, and MAOIs
7. Patient has received treatment with stem cells, deep brain stimulation, transcranial magnetic stimulation, or transcranial direct current stimulation for treatment of abnormal movements or CP within 6 months of the screening visit, or the patient is not in a stable clinical condition.
 8. Patient has recent surgical procedure or is anticipated to have a surgical procedure during the study that, in the opinion of the investigator, makes the patient unsuitable for the study.
 9. Patient has a severe mental disability or an unstable or serious medical illness (eg, epilepsy) at screening or baseline that, in the opinion of the investigator, could jeopardize or would compromise the patient's ability to participate in this study.
 10. Patient has a QT interval corrected for heart rate using Fridericia's formula (QTcF) value >450 msec on 12-lead ECG at screening.
 11. Patients with a history of torsade de pointes, congenital long QT syndrome, bradyarrhythmias, other cardiac arrhythmias, or uncompensated heart failure.
 12. Patient has evidence of diminished hepatic function, as indicated by the following:
 - Aspartate aminotransferase (AST) or alanine aminotransferase (ALT) $>2.5 \times$ the upper limit of the normal range (ULN) at screening
 - Alkaline phosphatase (ALP) or total bilirubin $>2 \times$ ULN at screening
 - Note: Patients with Gilbert's syndrome are eligible to participate if approved by the medical monitor.
 - Note: Patients with abnormalities in 2 or more of the following clinical laboratory parameters must be approved for enrollment by the medical monitor: AST, ALT, ALP, and total bilirubin.
 13. Patient has evidence of clinically significant renal impairment, indicated by a serum creatinine $>1.5 \times$ ULN at screening.
 14. Patient has a known allergy to any of the components of the IMP.
 15. Patient has participated in an investigational drug or device study and received IMP/intervention within 30 days or 5 drug half-lives of screening, whichever is longer.
 16. Patient is pregnant or breastfeeding.
 17. Patient has a history of or acknowledges alcohol or other substance abuse in the 12 months before screening.
 18. Patient has a positive urine drug screen test result (with exception of medications listed in [Table 10 of Appendix H](#)). Any request to include a patient with a positive urine drug screen test result should be discussed with, and approved by, the medical monitor. Refer to Section [7.5.2.2](#) (urine drug screen) for more details.

4.3. Withdrawal Criteria and Procedures for the Patient

Patients are expected to participate in this study for its entire duration and perform the scheduled visits and procedures.

During the titration period, an optimal dose should be sought for each patient. Throughout the maintenance period, patients will continue to receive the optimal dose determined during titration. If a patient experiences a “clinically significant” adverse event attributable to the IMP, the investigator will first determine if a dose reduction (to the previous dose level) or suspension is necessary and possible (Section 5.8). Each patient is free to withdraw from the study or discontinue from IMP at any time, without prejudice to their continued care, but every effort should be made to determine the reason for discontinuation.

Every effort should be made to ensure that patients comply with study visits and procedures, as detailed in the protocol. Patients must be withdrawn from the study if any of the following events occur:

1. Patient or parent(s)/legally acceptable representative withdraws consent or requests discontinuation from the IMP or withdrawal from the study for any reason.
2. Patient develops an illness that would interfere with his/her continued participation.
3. Patient is noncompliant with the study procedures and assessments or administration of IMPs in the opinion of the investigator.
4. Patient takes prohibited concomitant medications as defined in this protocol (see [Appendix H](#)).
5. Patient engages in alcohol or other substance abuse.
6. A female patient has a confirmation of pregnancy during the study from a positive pregnancy test.
7. The sponsor requests withdrawal of the patient.
8. Patient experiences an adverse event or other medical condition that indicates to the investigator that continued participation is not in the best interest of the patient.
9. The patient experiences a serious adverse event or pregnancy, or in cases when the investigator deems it necessary to unblind the patient’s IMP assignment to make treatment decisions.
10. Patient has evidence of diminished hepatic function based on the following liver function laboratory test results:
 - a. AST or ALT $>2.5 \times$ ULN
 - b. ALP or total bilirubin $>2 \times$ ULN
11. Patient develops Neuroleptic Malignant Syndrome (NMS)
12. If a post-baseline QTcF value >500 msec or change from screening >60 msec is found, the investigator should repeat the ECG assessment twice more and compare the average of these 3 post-screening QTcF values to the pre-treatment QTcF values at screening. The

IMP must be stopped for any confirmed post-baseline QTcF average value >500 msec or average increase from screening >60 msec.

13. In patients who experience signs of suicidal ideation or behavior (Section 7.9), the investigator should consult with the medical monitor to determine whether the patient should continue in the study.

In addition, a patient may be withdrawn from the study as described in Sections 3.4, 3.5, and 5.10 and Appendix C.

Because the statistical analysis of the primary endpoint of this study includes the assessment of randomness of missing data (Section 9.5.2.1), the most accurate as possible determination of the reason for ET is very important. Investigators should make every effort to obtain accurate information on patients in the case of withdrawal from the study or discontinuation from IMP. Results of any evaluations and observations, together with a narrative describing the reason(s) for withdrawal from the study or discontinuation from IMP, must be recorded in the source documents. The case report form (CRF) must document the primary reason for withdrawal from the study or discontinuation from IMP.

See Appendix G for information regarding how the study will define and address lost to follow-up patients to help limit the amount and impact of missing data.

If the reason for withdrawal from the study or discontinuation from IMP is an adverse event and/or clinically significant abnormal laboratory test result, monitoring will be continued as applicable (eg, until the event has resolved or stabilized, until the patient is referred to the care of a health care professional, or until a determination of a cause unrelated to the IMP or study procedure is made). If a patient is withdrawn wholly or in part because of an adverse event, the specific event or test result (including repeated test results, as applicable) must be recorded both on the source documentation and in the adverse events page and termination page of the CRF.

The patient will be monitored at the discretion of the investigator (eg, until the event has resolved or stabilized, until the patient is referred to the care of a health care professional, or until a determination of a cause unrelated to the IMP or study procedure is made). The investigator must inform the clinical project physician/clinical leader as soon as possible of any patients who are being considered for withdrawal due to adverse event(s). Additional reports must be provided when requested.

If a patient is withdrawn from the study for multiple reasons that also include adverse events, the relevant page of the CRF should indicate that the withdrawal was related to an adverse event. An exception to this requirement will be the occurrence of an adverse event that, in the opinion of the investigator, is not severe enough to warrant discontinuation but that requires the use of a prohibited medication, thereby requiring discontinuation of the patient. In such a case, the reason for discontinuation would be “need to take a prohibited medication” and not the adverse event.

All assessments should be performed according to the protocol on the last day the patient takes IMP, or as soon as possible thereafter.

For COVID-19 updates, refer to Appendix M.

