If patients endorse or report a children's C-SSRS suicidal ideation score of 3, 4, or 5, the patients will be evaluated immediately by the investigator and referred for psychiatric evaluation. The medical monitor will be immediately consulted. If it is determined by the investigator, the medical monitor, and consulting psychiatrist that exposure to the IMP may have contributed to a change in children's C-SSRS and/or increased depressive symptoms, study medication will be immediately discontinued and the patient will be terminated from the study. In cases where it is determined that IMP did not contribute to changes in depression or suicidality, the investigator will consult with the medical monitor, consulting psychiatrist, and/or sponsor to determine whether the patient should continue in the study.

If patients report any suicidal behavior that is an actual attempt as assessed in the children's C-SSRS, they will be evaluated immediately by the investigator, referred for psychiatric evaluation, and terminated from the study.

If patients report any suicidal behavior that is interrupted, aborted, or preparatory as assessed in the children's C-SSRS, they will be evaluated immediately by the investigator and referred for psychiatric evaluation. In cases where it is determined in the psychiatric evaluation that IMP did not contribute to changes in suicidal behavior, the investigator will consult with the medical monitor, consulting psychiatrist, and/or sponsor to determine whether the patient should continue in the study.

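### Section 4.3 item 13 makes every sign of suicidality a consultation on continuing, while Section 7.9 requires termination in two classes and leaves one branch without an outcome

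*Protocol*

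**What the plan says.** Section 4.3 introduces its list of withdrawal criteria with "Patients must be withdrawn from the study if any of the following events occur". Item 13 of that list reads "In patients who experience signs of suicidal ideation or behavior (Section 7.9), the investigator should consult with the medical monitor to determine"; the matter to be settled is continued participation. It covers ideation and behavior together, does not distinguish grades, and does not single out an actual attempt.

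Section 7.9 is graded by children's C-SSRS finding:

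- **Ideation items 1 or 2:** the case is discussed with the medical monitor, re-evaluated in clinic within 2 to 3 days, and treated on the investigator's judgment.
- **Ideation 3, 4 or 5:** immediate evaluation, psychiatric referral and consultation of the medical monitor. If the investigator, medical monitor and consulting psychiatrist find that the product may have contributed, dosing stops at once and the patient leaves the study. If they find that it did not, continuation is decided by consultation.
- **Actual attempt:** "they will be evaluated immediately by the investigator, referred for psychiatric evaluation, and terminated from the study".
- **Interrupted, aborted or preparatory behavior:** the rule opens "If patients report any suicidal behavior that is interrupted, aborted, or preparatory as assessed in the" children's C-SSRS, and requires immediate evaluation and psychiatric referral. Continuation is then addressed by one sentence only, which begins "In cases where it is determined in the psychiatric evaluation that IMP did not contribute to changes in suicidal behavior" and leads to a consultation.

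A general sentence in 7.9 also asks that discontinuation be considered in patients with signs of ideation or behavior.

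**The concern.** Site staff look in Section 4.3 for the rules on who leaves the study. A reader who acts on item 13 as written treats continuation after an actual attempt as open to discussion. A reader who acts on 7.9 does not. Both are following the protocol. The patients are children and adolescents, and 7.9 itself names suicidality as something the sponsor wants monitored, so different handling of the same event at different centers is a patient-safety matter first.

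There is also a link to the analysis. Section 4.3 stresses that the reason for early termination must be recorded accurately because the primary analysis classifies missing data by it. Section 9.3.1 does not require patients who stop the product to return at week 15. The rule a center follows can therefore decide whether a patient has an observed or an imputed week 15 value.

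**Working it through.** No arithmetic applies. The check sets item 13 of Section 4.3 beside Section 7.9, one event class at a time.

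| Event class | 4.3 item 13 | 7.9 | Result |
|---|---|---|---|
| Ideation 1 or 2 | Consult medical monitor on continuing | Discuss with medical monitor, re-evaluate, treat | Compatible |
| Ideation 3 to 5, product may have contributed | Consult on continuing | Stop dosing and terminate | **Conflict** |
| Ideation 3 to 5, product did not contribute | Consult on continuing | Consult on continuing | Compatible |
| Actual attempt | Consult on continuing | Terminate | **Conflict** |
| Interrupted, aborted or preparatory, product did not contribute | Consult on continuing | Evaluate, refer, consult on continuing | Compatible |
| Interrupted, aborted or preparatory, product contributed | Consult on continuing | Evaluate and refer; continuation not addressed | **Gap in 7.9** |

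The count is two conflicts, one gap and three compatible classes.

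On the first conflict, 7.9 does involve the medical monitor for ideation 3 to 5, so the two consultations could be taken for the same step. They are not. In 7.9 the joint judgment is about whether the product may have contributed, and once that is answered yes the outcome is fixed. In item 13 the consultation is about whether the patient continues, and nothing is fixed.

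On the gap, 7.9 writes out both causality branches for ideation 3 to 5 but only one for interrupted, aborted or preparatory behavior. The omission shows from the section's own structure.

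Section 4.3 also does not fit together internally. The stem announces events that require withdrawal, whereas item 13 prescribes a discussion that may end in either direction. Item 12 (QTcF) is procedural too, but it closes with a mandatory stop of the product once the finding is confirmed. Item 13 has no such end point.

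**The case against.** The best defense is that item 13 cites Section 7.9, so a reader is sent to the graded rules, and a specific rule normally prevails over a general pointer. The Amendment 05 summary of changes gives alignment with 7.9 as the reason for adding item 13, which supports that intention. But the citation is attached to the event, while item 13 goes on to state an action of its own. Neither section says which one governs.

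Other routes to withdrawal exist. Item 8 covers adverse events that make continuing contrary to the patient's interest, and item 9 covers serious adverse events. Neither names suicidality, and a further route out of the study does not reconcile item 13 with 7.9.

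Part of the defense stands. The patient in the incomplete branch is not left without any action: 7.9 requires evaluation and psychiatric referral whatever the cause and asks that discontinuation be considered, and item 13 supplies a consultation. What is missing is a continuation outcome in 7.9.

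Three stronger readings are tempting and are not supported:

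- A reader might infer from the stem that ideation 1 or 2 forces withdrawal and so contradicts 7.9. Item 13's own words call for a consultation, which fits 7.9 for that class. The awkward stem is a drafting fault, not a second rule for these patients.
- A reader might infer a contradiction with exclusion criterion 4, "Patient has a history of a previous actual, interrupted, or aborted suicide attempt based on medical or psychiatric history or the C-SSRS". Entry and continuation are separate decisions, and the protocol sets them differently elsewhere: a QTcF above 450 msec excludes at screening, while the on-study stopping limit is above 500 msec or a rise of more than 60 msec.
- A reader might infer that every patient with a positive C-SSRS is affected, or express the effect as a share of each arm. Three of the six classes agree. The scale is given only to patients aged at least 12, or 11 and turning 12 during the study. No event rate is stated.

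**Conclusion.** The point holds in this form. Item 13 of Section 4.3 and Section 7.9 give different actions for two event classes: an actual attempt, and ideation of 3 to 5 to which the product may have contributed. Section 7.9 also lacks a continuation outcome where the product contributed to interrupted, aborted or preparatory behavior. Item 13 further sits badly under a stem that requires withdrawal.

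The size is two conflicts and one gap among six classes. The number of patients, and any effect on the primary result, cannot be estimated from the protocol. Section 9.3.1 has the missing-data classification reviewed blinded and case by case, so the analytic consequence is a possible route and not a demonstrated bias. The case for correction rests on safety and on uniform conduct across centers.

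The conclusion assumes that item 13 is read as written, with its citation identifying the event and not replacing the action. It makes no judgment on which clinical rule is right.

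**What to change.** Reconcile the Section 4.3 stem, item 13 and Section 7.9 so that each event class has one stated action. One way is for item 13 to defer explicitly to the graded rules in 7.9 and state no action of its own, under a stem worded to admit conditional criteria. In 7.9, write the missing branch for interrupted, aborted or preparatory behavior to which the product contributed, and name who makes that determination. Which outcome applies in each class is for the sponsor's clinicians to settle.

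The cost is amendment wording in two sections. No visit, scale, sample size or analysis changes.

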4.4. Replacement of Patients

A patient who is enrolled but does not complete the treatment period will not be replaced.

4.5. Rescreening

A patient who is screened but not enrolled (eg, because inclusion and exclusion criteria were not met or enrollment did not occur within the specified time) may be considered for rescreening 1 time if there is a change in the patient’s medical background or other relevant change. (Note: the medical monitor should approve rescreening after review of the enabling reasons.)

Patients may have individual parameters retested at the discretion of both the investigator and the sponsor.

If the patient is rescreened, an informed consent form (ICF) will need to be re-signed.

For COVID-19 updates, refer to [Appendix M](#).

